2.2 Study Objectives

The primary objective of this trial is to evaluate the potential of dalcetrapib to reduce cardiovascular morbidity and mortality (cardiovascular [CV] death, resuscitated cardiac arrest, non-fatal myocardial infarction [MI] and non-fatal stroke) in subjects with a documented recent ACS and the AA genotype at variant rs1967309 in the ADCY9 gene.

The secondary objective of this trial is to evaluate the potential of dalcetrapib to reduce other clinically important events, such as hospitalization for ACS (with ECG abnormalities) or unanticipated coronary revascularization as well as hospitalization for new or worsening heart failure, in combination with the primary endpoint.

Additional objectives of this trial are as listed below:

- Evaluation of the effects of dalcetrapib on lipids and high-sensitivity C-reactive protein (hsCRP) in this population
- Assessment of the long-term safety profile of dalcetrapib, including on diabetes, in this population

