## 5.3 Assessments and Procedures During the Double-blind Treatment Period

Subjects will visit the study clinic 1 month and 6 months after randomization and every 6 months thereafter. With the exception of the screening visit, subjects should ideally be in a fasting state (minimum of 10 hours) for all visits requiring a blood draw (Visits 2 and 5) to be submitted to the central lab. Serum creatinine, HbA1c, fasting lipids and hsCRP will be evaluated for all subjects at Visits 2 and 5. If the patient forgot to fast or fasted for less than 10 hours, the sample should still be collected and sent to the central lab for analysis and documented accordingly in the CRF. At each site visit (and phone visit) after randomization, subjects will be assessed for the occurrence of adverse events and endpoint events.

Subjects will receive a new drug supply at each visit except at visit 3 (1 month) and visit 4 (3 month phone call). At each visit subjects will be required to bring in old unused drug for

assessment of compliance and the importance of compliance to study medication is to be emphasized.

All study assessments will be performed and lab samples will be collected as outlined in Table 1, Schedule of Assessments.

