#### 5.8.4.1 Serum Creatinine and HbA1c

Blood draw for serum creatinine and HbA1c will be obtained according to the schedule summarized in Table 1 and analyzed by the central laboratory. All clinically significant changes from randomization to trial completion should be reported as an AE in the source data and the eCRF.

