5.1 Adverse Events

An AE is any untoward medical occurrence in a subject or clinical investigation subject administered a pharmaceutical product and which does not necessarily have a causal relationship with this treatment. An AE can therefore be any unfavorable and unintended sign, including an abnormal laboratory finding, symptom, or disease temporally associated with the use of an investigational product, whether or not considered related to the investigational product. Pre-existing conditions that worsen during a study are to be reported as AEs.

AEs will be collected throughout the study after randomization. At each visit starting at Visit 3 (Month 1), the investigator will ask the subject if any untoward medical event occurred since the last visit. For each event, the date of onset and end, intensity, relationship to study medication, and outcome will be recorded on the eCRF.

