5.5 Laboratory Parameters

Blood samples are to be collected at Visit 2 (Day 0) and Visit 5 (Month 6) for the analysis of serum creatinine and hemoglobin A1c (HbA1c) (central lab). All adverse clinically significant changes from randomization to trial completion should be reported as an AE in the source data and the eCRF.

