5.6 New Onset Diabetes

New onset diabetes (NOD) is defined as a subject:

- without a history of diabetes as reported on the eCRF
- with HbA1c less than 6.5%, and
- without hypoglycemic medications

at the time of randomization, who meet one of the following criteria post-randomization:

- HbA1c value \geq 6.5%
- new diagnosis of type 2 diabetes mellitus (T2DM) defined as the occurrence of a diabetes-related adverse event
- use of a hypoglycemic medication

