6.5.5 New Onset Diabetes

Proportion of subjects with NOD will be compared between treatment groups using a Cochran-Mantel-Haenszel test, accounting for the two stratification factors. This analysis will be done for the ITT population, among the subjects with no diabetes at baseline.

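### The new-onset diabetes analysis cannot separate an early laboratory effect from a long-term clinical one, because scheduled HbA1c sampling stops at month 6 and the test ignores follow-up time

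*SAP*

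**What the plan says.** **Objective.** Protocol 2.2 lists long-term safety without mentioning diabetes. SAP 2.2 widens it: "Assessment of the long-term safety profile of dalcetrapib, including on diabetes, in this population".

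**Sampling.** SAP 5.5: "Blood samples are to be collected at Visit 2 (Day 0) and Visit 5 (Month 6) for the analysis of serum creatinine and hemoglobin A1c". Protocol 5.3 agrees: "Serum creatinine, HbA1c, fasting lipids and hsCRP will be evaluated for all subjects at Visits 2 and 5". In the schedule of assessments (Protocol Table 1, SAP Table 1) the central laboratory row is empty for months 12 to 36 and for the end-of-study visit.

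**Definition.** Under SAP 5.6 a subject free of diabetes at randomisation becomes an NOD case by any one of three routes:
- an HbA1c of 6.5% or more;
- a "new diagnosis of type 2 diabetes mellitus (T2DM) defined as the occurrence of a diabetes-related adverse event";
- "use of a hypoglycemic medication".

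The last two routes stay open to the end. SAP 5.1 states "AEs will be collected throughout the study after randomization", and SAP 6.3.5 records medication up to the end of study. Protocol 4.3 lets investigators check HbA1c locally when clinically indicated, but does not require it.

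**Analysis.** SAP 6.5.5: "Proportion of subjects with NOD will be compared between treatment groups using a Cochran-Mantel-Haenszel test, accounting for the two stratification factors". No time-to-event or exposure-adjusted analysis of NOD is specified. SAP 6.5.3 analyses HbA1c as change to 6 months, and promises creatinine means and medians across time.

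**The concern.** Before and after month 6 the NOD count rests on different kinds of ascertainment. At month 6 every subject is due a central HbA1c, so cases without symptoms can be found. Later, a case has to come to attention through an adverse event, a drug start or a discretionary local test, and a subject without symptoms can be missed.

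The planned analysis adds the two kinds of case together and divides by the number of subjects. Someone followed for 20 months and someone followed for 54 count alike, and so does someone who died or dropped out early. If the arms differ, the proportion does not say whether the difference came from the month-6 screen or built up over years of treatment. Reported under the SAP 2.2 objective, an early laboratory effect could be read as a long-term diabetes finding. A reassuring month-6 result could equally be read as long-term reassurance.

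Creatinine has a smaller version of the same problem: a summary described as running over time has one scheduled post-baseline point.

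**Working it through.** **The plan's own figures.** The plan gives no incidence, event count or power for NOD, so there is no NOD figure to reproduce. Its sample-size figure does reproduce and is not in dispute: 4 × (1.960 + 1.036)² / (ln 0.78)² = 35.91 / 0.0617 = 582 events.

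**Inputs for follow-up.**
- Total study length: about 54 months including enrolment (Protocol synopsis and 3.1).
- Recruitment: 2.8 years = 33.6 months (Protocol 8.2.1, SAP 6.1).
- Loss to follow-up: 1% per year (same sections).
- Last scheduled central draw: month 6, visit window ±3 weeks.
- Assumption not in the documents: uniform recruitment.

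**Planned follow-up and the share after month 6** (1 − 6 / follow-up):

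| Subject | Follow-up (months) | After month 6 | Draw 3 weeks late |
|---|---|---|---|
| Last enrolled | 54 − 33.6 = 20.4 | 71% | 67% |
| Mean | 54 − 33.6/2 = 37.2 | 84% | 82% |
| First enrolled | 54 | 89% | 88% |

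**Allowing for loss.** With loss rate l = −ln(1 − yearly loss), mean person-time is the average of (1 − e^(−l·f))/l over follow-up f from 1.7 to 4.5 years. The part before month 6 is (1 − e^(−0.5·l))/l.
- 1% yearly loss: mean 36.6 months, 84% after month 6.
- 5% yearly loss: mean 34.2 months, 83% after month 6.

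**A check that does not need uniform recruitment.** The schedule provides for subjects followed beyond 3 years, and SAP 6.5.1 has an exposure class above 1095 days. For a subject followed at least 36 months, month 6 is at most 6/36, or one sixth, of follow-up.

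**Illustration of where onsets fall.** NOD incidence is not given, so assume a constant 1% to 5% per year with no loss.
- 1% per year: 0.50% by month 6 and 3.06% by the end of follow-up; 1 − 0.50/3.06 = 84% of onsets come after month 6.
- 5% per year: 2.53% and 14.63%; 1 − 2.53/14.63 = 83%.

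Under a constant rate, most onsets would therefore fall where detection is clinical. This is not a count of missed cases, because the documents give no detection rate for either period.

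**The case against.** The case on the other side has real weight.

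- **The diabetes objective does not rest on one blood draw.** A reader might infer that it does. Two of the three NOD criteria are collected to the end of study, creatinine is not part of NOD, and SAP section 5 lists several other safety measures. This objection stands.
- **Follow-up after month 6 is not without laboratory data.** Local HbA1c is allowed, and SAP 5.6 does not restrict its HbA1c criterion to the central laboratory or to month 6. So one cannot say that the criterion can be met only then; the SAP simply does not say whether local values count. For the same reason Protocol 5.8.4.1 ("All clinically significant changes from randomization to trial completion should be reported as an AE in the source data and the eCRF") does not contradict the schedule, since local tests can reveal such changes. What is absent is scheduled central assessment.
- **54 months is not treatment length.** It is study duration including recruitment. Protocol 3.1 sets neither a minimum nor a maximum for treatment, and mean planned follow-up is 37.2 months.
- **No bias between arms is shown.** Allocation is 1:1, stratified and blinded, with the same schedule in both arms. One could speculate that fewer hospital contacts on the active arm would mean fewer chances to diagnose diabetes, but nothing in the documents establishes this. The CMH test remains valid for no effect.
- **The HbA1c change is already labelled as a 6-month result**, SAP 6.4.6 treats analyses outside the primary and secondary hierarchy as descriptive, and SAP 6.5 allows hazard-ratio methods for adverse event and laboratory differences of interest. The stakes are therefore lower. But SAP 6.5 leaves the scope of that work to be decided after a difference has been seen, so it does not pre-specify an NOD analysis.
- **Cox has its own weakness here.** Cases found only by the month-6 HbA1c have onset dates bunched at that visit. That is true, and it is why the split by source is needed and the CMH test should stay.

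**Conclusion.** The point holds as a limit on interpretation. There is one scheduled post-baseline central HbA1c and creatinine value, and about 84% of mean planned follow-up (71% to 89% across subjects) comes after it. The single NOD proportion merges a systematic early screen with later clinical detection and takes no account of planned follow-up of about 20 to 54 months, death or drop-out.

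The percentages rest on planning durations and uniform recruitment, not on actual enrolment dates. They describe where follow-up lies. They are not a bias, a loss of power or a number of missed cases.

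A reader might infer that the NOD test is invalid, or that a further blood draw is needed to rescue the objective. The documents do not support the first. The second would add a study procedure, whereas the ambiguity identified here can be reduced with data the trial already collects. The primary and secondary efficacy analyses are unaffected.

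**What to change.** In SAP 6.5.5:
1. Keep the CMH comparison.
2. Add time from randomisation to first NOD, using the stratified Cox model of SAP 6.4.1. The event date is the earliest qualifying adverse event onset, drug start or HbA1c sample. Censor at the last adverse event or medication assessment.
3. Report by arm, separately, the cases resting only on the month-6 HbA1c and those diagnosed by adverse event or drug start.
4. State whether local HbA1c values count towards the 6.5% criterion.
5. Base any long-term diabetes statement on the clinically diagnosed cases.

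In SAP 6.5.3, describe the creatinine summaries as baseline to month 6. The HbA1c wording there needs no change.

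**Cost.** No new data are needed: adverse event dates, medication records and the month-6 samples are already collected. The work is SAP wording and a little programming. The sponsor gives up some breadth in the laboratory safety claim. Two limits remain: HbA1c-only onsets will cluster at month 6, and a month-6 value that led to an adverse event report will count as clinically diagnosed, so the split shows the evidence for a case and not what prompted it.

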3. DATASETS ANALYZED

3.1 Exclusion of Data from Analysis

Subjects will be completely excluded from analyses if they do not satisfy the criteria for inclusion in the specified analysis population, as defined below. If a subject satisfies the criteria for inclusion in an analysis population then no data from that subject will be excluded from use.

3.3 Co-Diagnostic Analysis: Intent-to-Diagnose (ITD) Population

Subjects who provide written informed consent and have blood drawn for screening will be tested for rs1967309 of ADCY9 by the cobas® ADCY9 Genotype CTA. Subjects with AA genotype results will be allowed to proceed in the study and be further evaluated for eligibility into the study treatment phase and subjects with non-AA genotype will be excluded from the study; however, demographic data for both the AA and non-AA groups will be recorded for evaluation of the cobas® ADCY9 Genotype CTA as a companion diagnostic for dalcetrapib. Subjects who have a biologic sample obtained after Informed Consent will be included in the ITD population.

4. EFFICACY ENDPOINT

Study endpoints will be adjudicated by an independent Clinical Endpoint Committee (CEC) and endpoint classification forms will be provided as part of the eCRF. Procedures and processes for the CEC will be detailed in the CEC charter.

4.1 Primary Efficacy Endpoint

The primary endpoint of this study is the time from randomization to first occurrence of any component of the composite endpoint as adjudicated by the CEC. Components of the primary endpoint are:

- Cardiovascular death
- Resuscitated cardiac arrest
- Non-fatal MI
- Non-fatal stroke

Subjects who discontinued the study without experiencing one of these events will be censored at the time they were last known to be event-free. Time to event (or censoring) will be calculated as the difference (in days) between the adjudicated event date (or date of censoring) and the date of randomization + 1 day.

If a subject reports more than one of the above events, the earliest will be considered for the primary endpoint. If more than one event is reported with the same onset date, the subject will be assigned to the first event in the order of appearance above.

4.2 Secondary Efficacy Endpoints

The secondary endpoints of this study are time from randomization to first occurrence of each of the following composite endpoints, obtained from data adjudicated by the CEC:

- The composite of CV death, resuscitated cardiac arrest, non-fatal MI, non-fatal stroke, hospitalization for ACS (with ECG abnormalities), or unanticipated coronary revascularization
- The composite of CV death, resuscitated cardiac arrest, non-fatal MI, non-fatal stroke, or hospitalization for new or worsening heart failure

Note: Composite refers to the occurrence of any of the listed endpoints.

The rules described in 4.1 for censoring, for calculation of time to event (or censoring) and in case of multiple events per subject will similarly apply for the secondary endpoints.

4.3 Exploratory Efficacy Endpoints

Exploratory endpoints will include change from baseline to 6 months in:

- Blood levels of total cholesterol (TC), triglycerides (TG), low-density lipoprotein cholesterol (LDL-C) and high-density lipoprotein (HDL-C)

- Blood levels of hsCRP

5. SAFETY PARAMETERS

Safety will be assessed through the following: adverse events (AEs) and serious adverse events (SAEs), vital signs, physical examination, laboratory parameters and incidence of new onset diabetes.

5.1 Adverse Events

An AE is any untoward medical occurrence in a subject or clinical investigation subject administered a pharmaceutical product and which does not necessarily have a causal relationship with this treatment. An AE can therefore be any unfavorable and unintended sign, including an abnormal laboratory finding, symptom, or disease temporally associated with the use of an investigational product, whether or not considered related to the investigational product. Pre-existing conditions that worsen during a study are to be reported as AEs.

AEs will be collected throughout the study after randomization. At each visit starting at Visit 3 (Month 1), the investigator will ask the subject if any untoward medical event occurred since the last visit. For each event, the date of onset and end, intensity, relationship to study medication, and outcome will be recorded on the eCRF.

5.2 Serious Adverse Events

A SAE is any AE that at any dose fulfills at least one of the following criteria:

- is fatal [results in death; NOTE: death is an outcome, not an event]
- is life-threatening [NOTE: the term "Life-Threatening" refers to an event in which the subject was at immediate risk of death at the time of the event; it does not refer to an event that could hypothetically have caused a death had it been more severe].
- required in-subject hospitalization or prolongation of existing hospitalization;
- results in persistent or significant disability/incapacity;
- is a congenital anomaly/birth defect;
- is medically significant or requires intervention to prevent one or other of the outcomes listed above

It should be noted that implantable cardioverter-defibrillators (ICD) firings are not considered study endpoints but any ICD firing considered by the investigator as clinically relevant and meeting the criteria of an SAE will be reported as such.

5.3 Vital Signs

Seated blood pressure and pulse will be recorded after at least a 5-minute rest. Systolic/diastolic blood pressure and pulse will be recorded at Visit 2 (Day 0), Visit 3 (Month 1), Visit 5 (Month 6), Visit 6 (Month 12), Visit 7 (Month 18), Visit 8 (Month 24), Visit 9 (Month 30), Visit 10 (Month 36) and every 6 months thereafter until the end of the study (if possible).

5.4 Physical Examination

Physical examinations will include examination of the following body systems: general appearance, chest/lungs and cardiovascular, and will be performed at Visit 2 (Day 0) and at the end of the study. All adverse clinically significant changes from randomization to trial completion should be reported as an AE in the source data and the eCRF if an end-of-study Physical Exam is performed.

5.5 Laboratory Parameters

Blood samples are to be collected at Visit 2 (Day 0) and Visit 5 (Month 6) for the analysis of serum creatinine and hemoglobin A1c (HbA1c) (central lab). All adverse clinically significant changes from randomization to trial completion should be reported as an AE in the source data and the eCRF.

5.6 New Onset Diabetes

New onset diabetes (NOD) is defined as a subject:

- without a history of diabetes as reported on the eCRF
- with HbA1c less than 6.5%, and
- without hypoglycemic medications

at the time of randomization, who meet one of the following criteria post-randomization:

- HbA1c value \geq 6.5%
- new diagnosis of type 2 diabetes mellitus (T2DM) defined as the occurrence of a diabetes-related adverse event
- use of a hypoglycemic medication

6. STATISTICAL METHODOLOGY

6.1 Sample Size

The sample size calculation is based on the primary endpoint. Under the following assumptions:

- an expected relative risk reduction of 22% and
- a statistical significance defined as a two-sided alpha of 0.05

the trial would have more than 85% power if it continues until at least 582 subjects experience a primary CEC adjudicated event in the combined treatment groups.

The total number of subjects to randomize, 6000, was chosen so that the expected number of subjects with an event is at least 582. It is based on the following assumptions, which were reviewed according to actual and planned recruitment rate:

- a 2.8-year recruitment period;
- a 1% yearly lost to follow-up rate; and

- a 7% event rate at 2 years following randomization in the placebo group.

A total of 6149 are actually randomized in the study.

6.2 Statistical Considerations

Statistical analyses will be performed using SAS, Version 9.4 or higher, or other validated software. Unless otherwise specified, all statistical tests will be two-sided.

Study variables are to be presented with descriptive statistics. For continuous variables, the following will be reported: number of observations, mean, standard deviation, median, 25th and 75th percentiles (Q1 and Q3), minimum and maximum. For categorical variables, frequency and percentage will be reported.

Change from baseline is defined as: Post-baseline minus Baseline. Baseline is defined as randomization visit (V2).

6.2.1 Interim Assessment of Futility

On January 23, 2020, after the occurrence of approximately 70% (408) positively adjudicated primary study endpoints, an interim assessment of futility was conducted by the independent DSMB, based on the separate DSMB futility assessment SAP. Following this assessment, the DSMB recommended to continue the trial as planned.

Full details are described in the DSMB charter statistical analysis plan.

6.3 Study Subjects

6.3.1 Subject Disposition

The number of randomized subjects, number of randomized subjects who took study medication, number of randomized subjects completing the study and reasons for study discontinuation will be summarized by treatment group. The number of subjects with survival status assessed at the end of the study will also be presented.

A flow chart following the recommendations of the Consolidated Standards of Reporting (CONSORT) statement will also be provided.

A subject data listing of subject disposition will be provided.

6.3.2 Protocol Deviations

Major protocol deviations are defined as:

- A subject that did not meet entry criteria
- A subject that received the wrong treatment
- A subject that took an over-dose (more than 2 tablets per day)

- A subject that did not complete a planned revascularization procedure prior to randomization

Major protocol deviations will be captured in the clinical database within the standard eCRFs and included in a subject data listing.

6.3.3 Datasets Analyzed

The number of subjects in the ITT population will be summarized.

6.3.4 Demographic and Baseline Characteristics

Demographic data (age, sex [including reproductive status], race, ethnicity) and baseline characteristics which includes history of or current cardiovascular and non-cardiovascular diseases (diabetes), subject region, height, weight, body mass index, vital signs and smoking history will be presented using descriptive statistics by treatment group and overall for the ITT population. For age calculation, missing birth day will be replaced by 15 and missing birth day/month will be replaced by 01/JULY.

The following categories for the ACS index will be summarized:

- Diagnosis of spontaneous myocardial infarction
- Diagnosis of procedure-related myocardial infarction after percutaneous coronary intervention
- Hospitalization for ACS index event

Demographic data that was collected on subjects who provided informed consent and had a blood drawn for screening for rs1967309 of ADCY9 by the cobas® ADCY9 Genotype CTA, including subjects with AA genotype who were allowed to proceed in the study and subjects with non-AA genotype who were excluded from the study, will be reported by the *Roche Molecular Systems* team in a separate report.

